7. LIFESTYLE AND/OR DIETARY RESTRICTIONS

- Subjects should refrain from all illicit drugs throughout the study.
- Subjects should refrain from the ingestion of grapefruit containing products throughout the study.

• Subjects must fast from all food and drink for at least 8 hours prior to clinical laboratory assessment.

- Subject should not consume alcohol within 48 hours prior to study drug administration and throughout the study.
- Subjects will be allowed to eat normally during out-patient/washout time and will receive standard meal during inpatient stay. All drugs will be taken with light meal. They will be given a similar light standard meal within 30 minutes before each drug dosing (similar calories, carbohydrate, protein and fat ratio). Subjects will be allowed to eat 4 hours after study drug administration. Water or soft drinks without caffeine may be consumed 2 hours post-dose (after autonomic function testing). All subjects will receive the same meal.

• Total fluid intake may not exceed 3L per day during the dosing period.

8. PRODUCTS

• Artemether-lumefantrine

Artemether-lumefantrine is in the form of dispersible or standard tablets of 20 mg of artemether and 120 mg of lumefantrine in a fixed-dose combination formulation. The weight-based dosing schedule in appendix 3.

• Amodiaquine

Amodiaquine is in the form of dispersible tablets containing 76.5 mg amodiaquine co-blistered with sulfadoxine/pyrimethamine 250 mg/12.5 mg dispersible tablet (SPAQ-CO[®] Disp).

Amodiaquine dispersible tablets are tablets with yellow core debossed with "AM" on one side and a score line on the other side.

Sulfadoxine/pyrimethamine dispersible tablets are white round tablets, debossed with "SP" on one side and a score line on the other side.

This study will only use the amodiaquine. The weight-based dosing schedule in appendix 3.

All sulfadoxine/pyrimethamine tablets, unused Amodiaquine and unused Artemetherlumefantrine will be disposed following hospital standard procedures after study completion.

9. CONCOMITANT MEDICATIONS

The Principal Investigator must be informed as soon as possible about any medications taken by the subject from the time of screening until the last follow up visit or withdrawal visit. If a subject takes any concomitant medications taken during the study, it will be recorded in the CRF. Drug name, dose, frequency, route of administration and the start and end dates of administration are to be recorded

9.1. Prohibited Concomitant Medications

Use of prescription drugs including but not limited to drugs with antimalarial activities and any drug contraindicated with the investigational drugs e.g. quinacrine, mefloquine or nonprescription drug, including, vitamins, herbal and dietary supplements (including St. John's Wort) within 7 days (or 14 days if the drug is a potential enzyme inducer) or 5 half-lives (whichever is longer) prior to the first dose of study medication and for the duration of the trial including follow-up will be prohibited, unless in the opinion of the investigator, the medication will not interfere with the study procedures or compromise subject safety; the investigator will take advice from the manufacturer representative as necessary,

Subject should discuss with study team member before using over-the-counter medications during the study period except as needed to treat an adverse event.

If a subject takes a prohibited medication during the course of the study, the investigator and the statistician will determine if the subject should be withdrawn from the study or from the final pharmacokinetic analysis.

10. SUBJECT COMPLETION AND WITHDRAWAL

10.1. Subject Completion

Subjects who complete all the study visits and follow up per protocol, will be considered as having completed the study.

10.2. Subject withdrawn from the study

This includes the following:

- Subject voluntarily withdrew consent
- The Principal Investigator, sponsor withdrawing the study subject at his/her discretion for the benefit of the subject.

The reasons for withdrawal, or failure to provide a reason, will be documented by the investigator in the Completion/Withdrawal section of the CRF.

If a subject is prematurely discontinued from participation in the study for any reason, the investigator must make every effort to perform the follow up visit assessments, unless they have withdrawn consent.

10.3 Subject discontinues the study drugs

Such subjects will be followed up for safety data collection. Reasons for this scenario may include:

- Pregnancy
- Subject requests to discontinue study drugs
- Abnormal renal and hepatic laboratory result including;
 - o Any creatinine above 1.5 x ULN OR increase 0.3 mg/dL above baseline
 - o Any ALT or AST above 3 x ULN
 - o Any elevation in total and direct bilirubin 2x ULN
 - o Any AST or ALT above 2xULN and TBL >1.5xULN

o Any AST or ALT above 2xULN with the appearance of fatigue, nausea, vomiting, right upper quadrant pain or tenderness, fever, rash and/or eosinophilia (eosinophil percent or count above the ULN)

If the abnormalities are potentially caused by one of the study drug the research physician will decide whether the other regimen of the study drugs should be continued. All laboratory abnormalities will be assessed by a trained physician. In case of abnormalities, a medical history to assess exposure to substances (medication, alcohol and others) with known toxicity for instance liver or kidney will be performed. In addition, the physician can perform additional investigations that are deemed necessary to explain the laboratory abnormalities (such as hepatitis serology or urine analysis). The liver function and creatinine abnormalities will be monitored until resolution or the stabilization of the condition. In any case all laboratory values should have returned to normal (within the normal range in the case of full blood count values and at least <1.5 times the ULN in case of the biochemistry values) before the administration of the next treatment round.

- QTc interval abnormalities;
- QTc or QT interval longer than 500 milliseconds

A case by case judgement will be made on whether the subjects should be discontinued from the study completely. All other drugs known to prolong the QTc interval will be stopped. QTc intervals will be monitored continuously until normalisation of the QTc interval to below 450 milliseconds. Magnesium and potassium levels will be measured and deficiencies will be supplemented through intravenous or oral medication.

Unevaluable subjects may be replaced, according to the discretion of the investigators with another subject of the same population, if either sample size or completeness of dataset is compromised. All data will be listed and will be valid for clinical safety and tolerability evaluation.

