5. STUDY POPULATION

5.1. Number of Subjects

This study will enroll 16 healthy subjects both male and female, aged 18-60 years, at the pharmacokinetic unit Faculty of Tropical Medicine, Mahidol University. Subjects will be healthy HIV-1, hepatitis B and C uninfected individuals who comprehend the purpose of the study and have provided written consent. All subjects will undergo screening assessments (visit 1). Screening assessments (visit 1) may be carried out over more than one day, provided that all required assessments are completed within the 14 days prior to visit 2. If the interval between screening (visit 1) and day -1 visit 2 is three days or less, the clinical laboratory screening test result and serum pregnancy test result can be used for enrolment evaluation on day -1 visit 2. In such cases, these tests would not need to be repeated at day-1 visit 2.

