5.3. Exclusion Criteria

Subjects will not be enrolled into the study if they meet any of the following exclusion criteria:

- 1. Females who are pregnant, trying to get pregnant, or are lactating.
- 2. The subject has evidence of active substance abuse that may compromise safety, pharmacokinetics, or ability to adhere with protocol instructions.
- 3. A positive pre-study hepatitis B surface antigen, positive hepatitis C antibody, or positive human immunodeficiency virus-1 (HIV-1) antibody result at screening.
- 4. Subjects with a personal history of cardiac disease, symptomatic or asymptomatic arrhythmias, syncopal episodes, or additional risk factors for torsades de pointes (heart failure, hypokalemia) or with a family history of long QT syndrome, Brugada syndrome, or sudden cardiac death.
- 5. Abnormal serum creatinine (Scr) and estimated glomerular filtration rate (eGFR) <70 mL/min as determined by CKD-EPI equation
- 6. History of alcohol or substance abuse or dependence within 6 months of the study.
- 7. Use of prescription or non-prescription drugs except paracetamol at doses of up to 2 grams/day, including vitamins, herbal and dietary supplements (including St. John's Wort) within 7 days (or 14 days if the drug is a potential enzyme inducer) or 5 times the drug half-life (whichever is longer) prior to the first dose of study medication until the completion of the follow-up procedure, unless in the opinion of investigator, the medication will not interfere with the study procedures or compromise subject safety; the investigator will take advice from the manufacturer representative as necessary.
- 8. The subject has participated in a clinical trial and has received a drug or a new chemical entity within 30 days or 5 x half-life, or twice the duration of the biological effect of any drug (whichever is longer) prior to the first dose of study medication.
- 9. The subject is unwilling to abstain from ingesting alcohol within 48 hours prior to the first dose of study medication until collection of the final pharmacokinetic sample during each regimen.
- 10. Subjects who have donated blood to the extent that participation in the study would result in more than 300 mL blood donated within a 30-day period. Note: This does not include plasma donation.

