- 11. Subjects who have a history of allergy to the study drug or drugs of this class, or a history of drug or other allergy that, in the opinion of the investigator, contraindicates participation in the trial. In addition, if heparin is used during pharmacokinetic sampling, subjects with a history of sensitivity to heparin or heparin-induced thrombocytopenia should not be enrolled.
- 12. Lack of suitability for participation in this study, including but not limited to, unstable medical conditions, systemic disease manifested by tendency to granulocytopenia e.g. rheumatoid arthritis and lupus erythematosus that in the opinion of the investigator would compromise their participation in the trial.

- 13. AST or ALT >1.5 times the upper limit of normal (ULN)
- 14. Subjects with history of renal disease, hepatic disease, and/or cholecystectomy
- 15. Abnormal methemoglobin level (more than 3 mg/dL).
- 16. History of antimalarial drugs use including but not limited to mefloquine, chloroquine, primaquine, artesunate, piperaquine and pyronaridine treatment within 6 months.
- 17. Subject who have received quinacrine in last 30 days.
- 18. Subject has been included in other clinical trials in last 6 months.

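### Protocol 10.3: the <1.5 x ULN condition for the next treatment round is looser than the section's own 0.3 mg/dL creatinine stop rule and sets no lower limit for potassium or magnesium

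*Protocol*

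**What the plan says.** Protocol 10.3 gives as a reason to discontinue study drug "Any creatinine above 1.5 x ULN OR increase 0.3 mg/dL above baseline". For the liver it gives "Any ALT or AST above 3 x ULN", with lower limits when bilirubin or symptoms are also abnormal. On follow-up it says: "The liver function and creatinine abnormalities will be monitored until resolution or the stabilization of the condition".

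It then sets the condition for the next round: "In any case all laboratory values should have returned to normal". A bracket explains what that means. Blood counts must be inside the normal range; biochemistry must be "at least <1.5 times the ULN in case of the biochemistry values". Section 6.3.5 counts creatinine, potassium and magnesium among the chemistry tests, so the multiple applies to them.

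Section 5.3, criterion 4, excludes subjects with added risk factors for torsades de pointes and names hypokalemia as one. Section 10.3 provides for supplementing low potassium and magnesium, but only under QTc abnormalities.

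**The concern.** A restart condition should be at least as strict as the stop rule it follows. For the liver tests it is. For the 0.3 mg/dL creatinine limb it is not, so the number given to the physician does not separate a creatinine rise that has resolved from one that has persisted. For potassium and magnesium, where a low value is the cardiac concern, an upper multiple tests the wrong end of the range.

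The restart condition is also where the creatinine rule does its work. Under Appendix 2 and section 6.1.2, chemistry is scheduled on Day -1, on Day 3 and at follow-up from Day 7, while doses run from 0 h to 60 h. No scheduled chemistry falls between the first and last dose of a round. On scheduled tests, the creatinine rule can therefore act only on the next round, and the looser limit applies there.

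What is at stake is subject safety before Visits 3 and 4, and above all before Visit 4, when both treatments are given together. Section 13.2 reports QTc prolongation in 7 of 20 amodiaquine-treated patients. No sample size, power or error rate is affected.

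**Working it through.** **Inputs.** From Protocol 10.3: stop at baseline + 0.3 mg/dL; restart below 1.5 x ULN. The documents give no laboratory reference limits. As assumptions I take a creatinine ULN of 1.1 to 1.3 mg/dL and a baseline of 0.7 to 1.0 mg/dL.

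**Creatinine, general result.** Write b for baseline. The stop value meets the restart limit when b + 0.3 < 1.5 x ULN. The worst case with b at or below ULN is b = ULN, which requires 0.5 x ULN > 0.3, or ULN > 0.3/0.5 = 0.6 mg/dL. This does not depend on the assumed ranges.

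**Creatinine, illustration.**

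| Assumed ULN | Restart limit, 1.5 x ULN | Stop value, b = 0.7 | Stop value, b = 1.0 |
|---|---|---|---|
| 1.1 | 1.65 | 1.0 (0.91 x ULN) | 1.3 (1.18 x ULN) |
| 1.2 | 1.80 | 1.0 (0.83 x ULN) | 1.3 (1.08 x ULN) |
| 1.3 | 1.95 | 1.0 (0.77 x ULN) | 1.3 (1.00 x ULN) |

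Every stop value lies below the restart limit. At b = 0.7 it is also below ULN, so it would pass even if the biochemistry had to be strictly normal.

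**Liver tests, for comparison.** The restart limit of 1.5 x ULN is tighter than the ALT/AST limits (3 x and 2 x) and the bilirubin limit (2 x), and equals the total bilirubin limit (1.5 x) in the combined rule. It also matches the entry limit for AST and ALT in section 5.3, criterion 13. Nothing needs to change here.

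**Potassium and magnesium.** No low value can fail a limit of the form <1.5 x ULN. The upper end is not useful either: with an assumed potassium ULN of 5.0 to 5.5 mmol/L the limit is 7.5 to 8.25, and with an assumed magnesium ULN of 2.2 to 2.6 mg/dL it is 3.3 to 3.9.

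**Baseline.** The stop rule needs a reference value, and neither document names one for creatinine. Candidates are screening and Day -1 of Visits 2, 3 and 4. Section 5.1 adds that, when screening is three days or less before Day -1, "the clinical laboratory screening test result and serum pregnancy test result can be used for enrolment evaluation on day -1 visit 2". The adverse event text in sections 11 and 11.2 uses the word for the time before the first dose or the start of the study, which points to a pre-study value. SAP Table 1 uses the word only in its title.

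**The case against.** The strongest reply is that the limit is a floor and not a permission. The sentence opens with in any case and the bracket says at least, so it adds to other controls:

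- A physician assesses all laboratory abnormalities and decides on the other regimen where a study drug may be the cause.
- Day -1 chemistry must be reviewed before Day 0 dosing (section 6.1.2).
- A 24-hour urine creatinine clearance is done on Day -1 and Day 2 of each admission, although no threshold is attached to it.
- ECG and Holter recordings are frequent, and the washout exceeds 6 weeks.
- Laboratory abnormalities that arise or worsen on study are adverse events and are managed clinically (section 11.2).

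All of this stands and keeps the practical risk low. It also rules out three stronger readings that a reader might infer:

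- *The protocol allows re-dosing on a persisting creatinine rise simply because 1.5 x ULN is met.* It does not: the physician's decision remains, and nothing withdraws the 0.3 mg/dL limb at Visits 3 and 4.
- *Baseline may be reset at each admission, so that small rises add up unseen.* No text says so, and the adverse event wording favours a pre-study value.
- *A low potassium would go unnoticed before the combination.* It would be on the Day -1 report, which must be reviewed, and a low value is not normal in the ordinary sense.

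What the reply does not supply is a number. The only numeric restart limit for chemistry is one that the 0.3 mg/dL stop value already meets. The bracket also weakens the word normal for biochemistry while keeping the full range for blood counts.

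**Conclusion.** The point holds as a mismatch inside section 10.3, with low practical risk. The numeric condition for the next round is already met by a subject stopped on the 0.3 mg/dL creatinine limb, for any baseline at or below ULN and any ULN above 0.6 mg/dL. It sets no lower limit for potassium or magnesium. The creatinine result is algebra on the protocol's own limits; only the illustrative values rest on assumed reference ranges. The undefined creatinine baseline is a smaller, related gap, because the adverse event text leans towards a pre-study value without fixing one. The liver limits are sound.

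**What to change.** In section 10.3, state that before dosing at Visits 3 and 4, on Day -1 chemistry:

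- creatinine is <1.5 x ULN and less than 0.3 mg/dL above baseline, where baseline is the last value before the first Visit 2 dose (the screening value if Day -1 chemistry was not repeated under section 5.1);
- potassium and magnesium are within the normal range, or are corrected before dosing;
- liver tests stay at <1.5 x ULN.

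No new test or blood draw is needed, since Day -1 chemistry at Visits 3 and 4 is already taken and reviewed before dosing. The downside is an occasional delayed period or, rarely, a missed one, possibly for a creatinine still within the normal range. This matters most at Visit 4: a subject who misses it contributes no combination value to any of the 18 ratios in SAP Table 3 (6 analytes x 3 parameters), in a trial of 16. Allowing electrolytes to be corrected before dosing keeps that loss small.

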10.4 Study Halting Rules

When three subjects experience adverse events of grade 3 or above that are "probably related or related" to the study drug, administration of study drug(s) will be halted and the investigator team will stop recruiting new study subjects promptly. Enrolled subjects who do not experience adverse event of grade 3 or above will receive study drug(s) until the study ends.

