All laboratory assessments (chemistry, hematology, FBS and urinalysis) must be drawn in the fasting state (8 hours fast). Results of these tests are to be available and reviewed prior to each subject receiving the study drug on day 0.

Note: At all visits the remaining blood serum will be frozen and stored for use in an exploratory analysis evaluating independent renal markers against standard blood urea nitrogen/ creatinine levels as markers of renal toxicity.

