6.3 Safety Assessments

The physician or qualified clinical study staff will review the data at intervals throughout each study period.

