11. ADVERSE EVENTS AND SERIOUS ADVERSE EVENTS

The investigator is responsible for the detection and documentation of events meeting the criteria and definition of an adverse event (AE) or serious adverse event (SAE), as provided in this protocol.

All SAEs and AEs will be promptly reported from first dose of study drug administration to discontinuation of the subject from study participation. Any events occurring between screening and first dose of study drug administration will be considered as baseline, preexisting conditions.

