11.3 Prompt Reporting of Serious Adverse Events

All SAEs should be reported promptly to medical monitor for the study within 24 hours for all SAEs to e-mail address: [contact].

If all information is not yet available then an initial report must be made within the timeframe. Further interim reports may be made if necessary or a final report when all relevant information is available.

Faculty of Tropical Medicine Ethic committee (FTM EC) will be notified within 5 official days for all SAEs.

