12.7. Interim analyses

No formal interim analysis is planned.

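### The halting rule in protocol 10.4 contradicts itself and, on its likely reading, lets unaffected healthy volunteers be dosed on after three related grade 3 or higher events with no pause or required review

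*Protocol*

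**What the plan says.** Protocol 10.4 is the only study-level stopping provision. It applies once three subjects have had adverse events of grade 3 or above judged probably related or related to study drug. The first sentence then states that "administration of study drug(s) will be halted and the investigator team will stop recruiting new study subjects promptly". The second states: "Enrolled subjects who do not experience adverse event of grade 3 or above will receive study drug(s) until the study ends". The section names no pause, reviewer, decision or restart condition.

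Other safety provisions in the protocol:

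- **6.1.2:** on a subject's laboratory tests, "Results of these tests are to be available and reviewed prior to each subject receiving the study drug on day 0".
- **6.3:** a physician or qualified staff will "review the data at intervals throughout each study period".
- **10.2:** the investigator or sponsor may end participation, "withdrawing the study subject at his/her discretion for the benefit of the subject".
- **10.3:** individual discontinuation criteria for renal, hepatic and QTc abnormalities, and a requirement that laboratory values recover before the next treatment round.
- **11:** "All SAEs and AEs will be promptly reported from first dose of study drug administration", with no recipient or deadline given.
- **11.3:** "All SAEs should be reported promptly to medical monitor for the study within 24 hours"; the ethics committee is told of SAEs within 5 official days.
- **12.7:** "No formal interim analysis is planned".

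SAP 3.5.3 tabulates and reviews adverse events but contains no stopping or restart provision.

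**The concern.** Two physicians at the site could act in opposite ways on the day the trigger is met, and both could cite 10.4. One would stop all dosing on the strength of the first sentence. The other would keep dosing everyone who is well on the strength of the second.

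The likely intent is that recruitment and the affected subjects stop while the rest continue. If so, the rule does little at the point where it should do most. Every subject receives the combination last, at visit 4. By the time most combination doses are due, recruitment may already be complete, so stopping it would protect almost nobody. The remaining subjects are healthy volunteers for whom 13.3 expects no direct benefit, and section 1 gives unanticipated adverse reactions from co-administration as a reason for the study. A cluster of three severe, drug-related events should lead someone to look at them together before anyone else is dosed.

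**Working it through.** Section 10.4 states no error rate, power or threshold probability, so there is no figure of the plan's own to reproduce. The check is mainly a comparison of provisions.

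**Step 1: can the two sentences of 10.4 both hold?**

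- If the halt applies to everyone, the second sentence is false, because unaffected enrolled subjects would not be receiving drug. There would be a stop, but no review or restart step.
- If the halt applies only to affected subjects and new recruits, both sentences hold. Dosing of unaffected subjects then continues without interruption.

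Only the second reading reconciles the text.

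**Step 2: does another section require a study-level review before dosing continues?**

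| Provision | What it covers | Required after the trigger, across subjects? |
|---|---|---|
| 6.1.2 laboratory review before day 0 | The subject's own results | No |
| 6.3 review at intervals | Data in general | No: not tied to the trigger or to a dosing decision |
| 10.2 withdrawal | One subject, discretionary | No |
| 10.3 discontinuation criteria and laboratory recovery | The subject's own results | No |
| 11 prompt AE reporting | All AEs | No: no recipient, deadline or decision |
| 11.2 clinical management of an AE | The affected subject | No |
| 11.3 medical monitor and ethics committee | SAEs | No: a notification, with no decision before others are dosed |
| 12.7 interim analysis | None planned | No |
| 13.7 monitoring visits | Conduct and records | No |
| SAP 3.5.3 | Tabulation and review of AEs | No |

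Section 11.4.1 says that a severe event is not necessarily a serious one. Three related grade 3 events could therefore meet the trigger without being reportable under 11.3.

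**Step 3: how many subjects could be affected?**

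Inputs: 16 subjects (section 4); 3 subjects to trigger (10.4); six doses per regimen, at 0, 8, 24, 36, 48 and 60 h (Table 2, Appendix 3).

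- Subjects outside the triggering three: 16 − 3 = 13, and 13/16 = 81%. This is an upper bound.
- Each of them awaiting visit 4 has 6 combination doses to come.

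**Step 4: what could a pause cost in precision?**

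A pause during a subject's 60 h course could remove that subject from the pharmacokinetic set, since 12.2 requires the full dose. I assume a paired analysis of the log ratio of combination to alone, with n − 1 degrees of freedom. The 90% CI half-width is then proportional to t(0.95, n − 1)/√n, and the within-subject SD cancels in the ratios.

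- n = 16: 0.4383
- n = 13 (the three affected subjects lost): 0.4943; 0.4943/0.4383 = 1.13
- n = 11 (two more lost to a mid-course pause): 0.5465; 0.5465/0.4943 = 1.11

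The fall from 16 to 13 could happen with or without the change. The further fall to 11 is the illustrative cost of a pause. It widens the interval by about 11% on the log scale and goes below the 12 subjects cited in 12.4 (13 − 12 leaves a margin of one).

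**Step 5: trigger wording.**

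The causality scale in 11.4.2 is Definite, Probable, Possible and None. The trigger's second term, related, is not one of these categories, so whether an event counts needs interpretation.

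**The case against.** The strongest reply is that the absence of a pause depends on a chosen reading; taken literally, the first sentence does stop study drug. That is so, and the consequence is stated here as conditional. It does not rescue the text, because the second sentence contradicts the literal reading and no review or restart step follows on either one.

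Second, the events would not go unexamined. The trigger cannot fire until investigators have graded each event, judged its causality and counted three subjects. Any qualifying event that is also an SAE reaches the medical monitor and the ethics committee. Under 10.3 the research physician decides whether the other regimen continues when a laboratory abnormality may be drug-related. These safeguards are real and narrow the gap. What remains missing is a required joint assessment with a dosing decision attached. The lack of an interim analysis adds little to this point, since that is a statistical procedure.

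Third, continuing unaffected subjects may be a deliberate choice, and 13.2 describes the reported effects as generally mild for one product and mainly mild to moderate for the other. That is a fair defence of the policy, but not of the wording. The first sentence would still need to say that only affected subjects stop.

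Fourth, 81% is only an upper bound. If the events arise late in visit 4, fewer subjects have doses left. The loss of two further subjects in step 4 is likewise an example, not a forecast. Both points stand.

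**Conclusion.** The concern holds and should be fixed. That 10.4 is inconsistent is certain from its own text. That it requires no pause and no joint review before unaffected subjects are dosed again follows on the only reading that reconciles its sentences, and nothing elsewhere in the protocol or SAP fills the gap.

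The exposure is at most 13 of 16 subjects, assuming full enrolment, doses still due for all 13, and no other grade 3 or higher event among them. The documents give no event rate, so no probability that the trigger fires is claimed. If it does not fire, no estimate or analysis changes. The individual safeguards, and that dependence on the trigger, are why this ranks as something to amend and not as a threat to the study's conclusions.

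**What to change.** Replace the second sentence of 10.4 with wording to this effect: *Once the trigger is met, no enrolled subject receives further study drug until the investigators and the medical monitor have completed a documented safety review; unaffected subjects may resume only if that review supports it.* In the same amendment, define the trigger by the 11.4.2 categories Definite or Probable. If the sponsor does intend only affected subjects to stop, the first sentence must say so.

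The edits are short, use people already in the study, and cost nothing unless the trigger fires. If it fires between visits, the cost is delay: the washout is set at more than 6 weeks with no stated maximum, so a pause does not breach it.

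If it fires during a dosing course, subjects may be lost from the pharmacokinetic set, with the effect on precision shown above. Sections 10.3 and 12.2 allow replacement at the investigators' discretion, but 10.4 stops recruitment and does not say whether a replacement counts as a new recruit. The amendment should settle that. A review that does not support resuming would end combination data from subjects not yet dosed at visit 4.
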